##### 5.4.2.1.1. Analysis for Supplementary Estimands

The analyses specified in Section 5.3.2.2.1 (Hypothetical Estimand) and Section 5.3.2.2.2 (Treatment Policy Estimand) for supplementary estimands will be applied to the following secondary endpoints:

- Proportion of participants achieving PASI 90 ( $\geq 90\%$  improvement from baseline in PASI) at Week 16
- Proportion of participants achieving PASI 100 (100% improvement from baseline in PASI) at Week 16
- Proportion of participants achieving an IGA score of cleared (0) or minimal (1) at Week 16
- Proportion of participants achieving an IGA score of cleared (0) at Week 16

#### 5.4.2.2. Continuous Endpoints

Unless otherwise specified, the analyses for continuous secondary endpoints at Week 16 will be based on the following strategies to handle ICEs and missing data.

- ICEs in categories 1 - 2 in the primary estimand (definitions in Section 5.4.1.2) will be handled with the Composite Strategy. Participants experiencing ICEs 1-2 will have a zero change (or zero improvement) from baseline assigned from that point onward.
- ICEs in category 3 in the primary estimand (definitions in Section 5.4.1.2) will be handled by the Treatment Policy strategy. The analysis will be performed using observed data regardless of intercurrent events.
- For participants experiencing multiple ICEs, an ICE in category 2 of the primary estimand will override an ICE in category 3.
- Missing data will not be imputed after applying the rules for intercurrent events.

To account for the missing data for continuous endpoints of change (or percent change) from baseline measured at more than one post-baseline visit, a MMRM will be used. In MMRM, missing data will not be imputed, but rather missing data will be accounted for through correlation of repeated measures in the model.

Treatment comparisons for the secondary continuous endpoints at Week 16 will be performed using a Mixed-Effect Model Repeated Measure (MMRM) model. The model has factors for treatment group, visit, baseline weight category ( $\leq 90$  kg,  $> 90$  kg), baseline value for the efficacy endpoint and treatment by visit interaction. Additionally, the MMRM model will be also performed with factors for treatment group, visit, baseline weight category ( $\leq 90$  kg,  $> 90$  kg), baseline value for the efficacy endpoint, treatment by visit interaction and additional interaction terms of baseline weight category by visit and baseline value by visit. An unrestricted (UN) variance-covariance matrix for repeated measures within a participant will be used. If the model with unstructured covariance structure does not converge, alternative covariance structures will be considered in the following order, with the first structure that converges being used in the analysis: heterogeneous Toeplitz, standard Toeplitz, and autoregressive of order 1.

## 5.5. Exploratory Endpoint(s) Analysis

**Objectives are:** (a) To evaluate the effect of JNJ-77242113 treatment on patient-reported psoriasis severity versus placebo and (b) To evaluate the effect of JNJ-77242113 treatment on dermatology-specific and general health-related quality of life versus placebo in participants with moderate-to-severe plaque psoriasis.

The exploratory endpoints to address these objectives are the following:

### **To evaluate the effect of JNJ-77242113 treatment on patient-reported psoriasis severity versus placebo**

1. Change from baseline in Psoriasis Symptoms and Signs Diary (PSSD) symptoms score at Week 16
2. Change from baseline in PSSD signs score at Week 16
3. Proportion of participants achieving PSSD symptoms score=0 at Week 16 among participants with a baseline symptoms score  $\geq 1$ .
4. Proportion of participants achieving PSSD signs score=0 at Week 16 among participants with a baseline signs score  $\geq 1$ .

### **To evaluate the effect of JNJ-77242113 treatment on dermatology-specific and general health-related quality of life versus placebo**

5. Proportion of participants achieving a DLQI of 0 or 1 at Week 16 among participants with baseline DLQI score  $> 1$

In addition to the primary and secondary efficacy endpoints, the analyses for exploratory efficacy endpoints (including the over time summaries through Week 16) will be performed. These efficacy endpoints include the endpoints related to

- PASI
- IGA
- BSA
- Patient-reported Outcomes

PSSD

DLQI

#### 5.5.1. Endpoint Definitions

##### 5.5.1.1. Psoriasis Area and Severity Index (PASI)

Refer to section 5.3.1 for details.

### **5.5.1.2. Investigator's Global Assessment (IGA)**

Refer to section 5.4.1.1.2 for details.

### **5.5.1.3. Body Surface Area (BSA)**

Refer to section 5.4.1.1.3 for details.

### **5.5.1.4. Psoriasis Symptom and Sign Diary (PSSD)**

The PSSD includes PRO questionnaires designed to measure the severity of psoriasis symptoms and signs for the assessment of treatment benefit (Feldman 2016). This study uses a 7-day recall version of the PSSD that asks the participant to answer the questions thinking about the last 7 days. The PSSD is a self-administered PRO instrument and includes 11 items covering symptoms (itch, pain, stinging, burning, and skin tightness) and patient-observable signs (skin dryness, cracking, scaling, shedding or flaking, redness, and bleeding) using 0 to 10 numerical rating scales for severity. Two subscores are derived each ranging from 0 to 100: the psoriasis symptom score and the psoriasis sign score. A higher score indicates more severe disease.

### **5.5.1.5. Dermatological Life Quality Index (DLQI)**

The DLQI is a dermatology-specific health-related quality of life (HRQoL) instrument designed to assess the impact of the disease on a participant's HRQoL (Finlay 1994). It is a 10-item questionnaire that assesses HRQoL over the past week and in addition to evaluating overall HRQoL, can be used to assess 6 different aspects that may affect quality of life: symptoms and feelings, daily activities, leisure, work or school performance, personal relationships, and treatment. The total score ranges from 0 to 30 with a higher score indicating greater impact on QoL.

## **5.5.2. Analysis Methods**

The efficacy data from all participants in FAS will be included and analyzed by study intervention group through Week 16.

Similar to the secondary efficacy analyses, the endpoints will be summarized by intervention group. Simple descriptive statistics, such as n, mean, SD, median, IQ range, minimum and maximum for continuous variables and counts and percentages for discrete variables will be used to summarize most data. All statistical testing will be performed at a 2-sided 0.1 significance level. Nominal p-values will be presented. No adjustments for multiple comparisons will be made for the secondary endpoints.

### **5.5.2.1. At Week 16**

The exploratory endpoints at Week 16 will be analyzed using the same main estimands and the same analysis methods described in section 5.4.1.2 and section 5.4.2 for secondary endpoints. The analysis strategy for ICEs and missing data will be handled in the same manner as the main estimand for the secondary analyses (section 5.4.1.2).

- Change from baseline in Psoriasis Symptoms and Signs Diary (PSSD) symptoms score at Week 16
- Change from baseline in PSSD signs score at Week 16
- Proportion of participants achieving PSSD symptoms score=0 at Week 16 among participants with a baseline symptoms score  $\geq 1$ .
- Proportion of participants achieving PSSD signs score=0 at Week 16 among participants with a baseline signs score  $\geq 1$ .
- Proportion of participants achieving a DLQI of 0 or 1 at Week 16 among participants with baseline DLQI score  $> 1$

#### 5.5.2.2. Over Time Summaries Through Week 16

In general, all endpoints with over time analyses will be descriptively summarized by treatment groups using descriptive statistics, such as mean, median, standard deviation, interquartile range, minimum and maximum for continuous variables, and counts and percentages for categorical variables.

Similar to the Week 16 analyses for the secondary continuous endpoints, MMRM model approach specified in Section 5.4.2.2 will be used for the overtime summaries through Week 16. Least Square means (LSmeans), LS means differences and their corresponding 90% confidence interval will be provided over time through Week 16 by visit and treatment group in addition to the descriptive summary statistics.

Additionally, graphical data displays may also be used to summarize the overtime data if applicable.

##### 5.5.2.2.1. Analyses Related to PASI

- The change from baseline in PASI total score will be summarized by treatment group over time through Week 16.
- The proportions of PASI 75 responders, PASI 90 responders, and PASI 100 responders; the proportions of PASI 75 responders, PASI 90 responders, and PASI 100 responders by weight ( $\leq 90$  kg,  $> 90$  kg) will be summarized by treatment group over time through Week 16.
- The proportions of participants achieving  $\geq 75\%$  improvement,  $\geq 90\%$ , or achieving 100% improvement from baseline in PASI disease component (Induration, Erythema, and Scaling) and region component (head, trunk, upper extremities, and lower extremities) will also be summarized at Week 16.

##### 5.5.2.2.2. Analysis Related to IGA

- The proportions of participants achieving an IGA score of cleared (0); IGA score of cleared (0) or minimal (1) and the proportion of participants achieving a IGA score of mild or better

( $\leq 2$ ) overall and by weight ( $\leq 90$  kg,  $>90$  kg) will be summarized by treatment group over time through Week 16.

#### 5.5.2.2.3. Analyses Related to BSA

- The change from baseline in BSA will be summarized by treatment group over time through Week 16.

#### 5.5.2.2.4. Psoriasis Symptom and Sign Diary

The analyses for PSSD data are specified below and in general can be summarized in 3 categories as follows:

(a) Proportion of subjects who achieved clinically meaningful improvement in PSSD symptom score, sign score, and each individual scale score.

- The threshold for a clinically meaningful change from baseline in PSSD scores is defined as a change of  $\geq 40$  points in PSSD symptom and sign scores, change of  $\geq 3$  points in bleeding and stinging scores, change of  $\geq 4$  points in itch, dryness, cracking, skin tightness, burning and pain scores, and change of  $\geq 5$  points in scaling, shedding or flaking and redness scores.
- These analyses include only subjects who had at least minimal severity by each corresponding measure at baseline, i.e., a score of  $\geq 40$  in PSSD symptom and sign scores,  $\geq 3$  in bleeding and stinging scores;  $\geq 4$  in itch, dryness, cracking, skin tightness, burning, and pain scores, and  $\geq 5$  in scaling, shedding or flaking and redness scores, respectively.

(b) The proportions of subjects who achieve a score of 0 in PSSD symptom score, sign score, and each individual scale score among those who have a baseline PSSD symptom score, baseline sign score, and each individual baseline scale score that is  $\geq 1$

(c) Change from baseline in PSSD symptom score, sign score, and each individual scale score

#### 5.5.2.2.5. Analyses Related to Psoriasis Symptom and Sign Diary

- The proportion of subjects with clinically meaningful improvement from baseline in PSSD symptom score, sign score, and each individual scale score at Week 16 will be compared between each of the JNJ-77242113 group and the placebo group among participants with at least minimal severity in PSSD individual scale scores at baseline.
- The proportion of subjects with clinically meaningful improvement from baseline in PSSD symptom score, sign score, and each individual scale score will be summarized among participants with at least minimal severity in PSSD individual scale scores at baseline by treatment group.
- The change from baseline in each PSSD individual scale score at Week 16 will be compared between each of the JNJ-77242113 groups and the placebo group.

- The proportions of participants who achieve a score of 0 in each individual PSSD scale score at Week 16 will be compared between each of the JNJ-77242113 groups and the placebo group among participants with a baseline PSSD individual scale score  $>0$ .
- The change from baseline in PSSD symptoms score, signs score, and each PSSD individual scale score will also be summarized at Week 8 by treatment group.
- The proportions of participants who achieve a PSSD symptoms score of 0, signs score of 0 and each individual scale score of 0 will be summarized at Week 8 among participants with a baseline PSSD symptoms score, baseline signs score  $>0$ , and baseline each individual scale score  $>0$  by treatment group.

#### 5.5.2.2.6. Analyses Related to DLQI

- The change from baseline in DLQI score will be summarized at Week 8 and Week 16; and the change from baseline in DLQI score at Week 16 will be compared between each of the JNJ-77242113 groups and the placebo group.
- The proportions of participants with DLQI score of 0 and 1 for the participants with baseline DLQI score  $>1$  will be summarized at Week 8.
- The proportion of participants with a reduction of 5 or more points in DLQI score for the participants with baseline DLQI score  $\geq 5$  at Week 16 will be compared between each JNJ-77242113 treatment group and the placebo group and will also be summarized by treatment group at Week 8.
- The change from baseline in DLQI component scores at Week 16 will be compared between each JNJ-77242113 treatment group and the placebo group.

### 5.6. Safety Analyses

All safety analyses will be performed using safety analysis set based on actual intervention received. No formal statistical comparison is planned.

For all continuous safety variables, descriptive statistics by intervention group will include the N, mean, standard deviation, median, minimum, and maximum. Categorical variables will be summarized by intervention group using frequency counts and percentages.

The cumulative safety data will be analyzed. Unless otherwise specified, tabular summaries of safety events are also presented as following:

Safety data through Week 20 will be summarized by following intervention group:

- Placebo
- JNJ-77242113 10 mg qd CCI
- JNJ-77242113 50 mg qd CCI
- Combined JNJ-77242113 groups

### **5.6.1. Extent of Exposure**

The extent of exposure will be summarized for randomized participants that received at least one study agent administration. Distribution of participants through Week 16 by study agent lot will be analyzed. In addition, the number (%) of participants receiving the study drug during double blind treatment phase will be summarized by treatment group.

The total duration of exposure to study medication (days), including days off medication, will be calculated as:

Total duration of exposure = last day of study medication - first day of study medication + 1.

### **5.6.2. Adverse Events**

The verbatim terms used in the CRF by investigators to identify adverse events will be coded using the Medical Dictionary for Regulatory Activities (MedDRA). Any AE occurring at or after the initial administration of study intervention is considered to be treatment emergent. If the event occurs on the day of the initial administration of study intervention, and either event time or time of administration are missing, then the event will be assumed to be treatment emergent. If the event date is recorded as partial or completely missing, then the event will be considered to be treatment emergent unless it is known to be prior to the first administration of study intervention based on partial onset date or resolution date. All reported treatment-emergent adverse events will be included in the analysis. For each adverse event, the number and percentage of participants who experience at least 1 occurrence of the given event will be summarized by intervention group.

Summary tables will be provided for treatment-emergent adverse events:

- AEs
- Serious AEs (SAEs)
- AEs leading to discontinuation of study intervention
- AEs of severe intensity
- AEs related to study intervention

In addition to the summary tables, listings will be provided for participants who:

- Had SAEs
- Had AEs leading to discontinuation of study intervention
- Had AEs of severe intensity
- Had AE for psoriasis

- Had suicidal ideation or suicidal behavior
- Had anaphylactic or serum sickness reactions

A listing of participants who died will be provided.

Since safety should be assessed relative to follow-up, most AE summary tables will include average weeks of follow-up for each intervention group.

### 5.6.3. Additional Safety Assessments

#### 5.6.3.1. Clinical Laboratory Tests

Clinical laboratory tests will be displayed for the participants included in the safety analysis set.

Descriptive statistics and graphical displays will be presented for selected chemistry and hematology laboratory tests at scheduled time points.

Change from baseline through Week 20 will be summarized for chemistry, and hematology tests and displayed by intervention group. Box plots of laboratory measurements and change from baseline will be provided for the selected laboratory measurement.

- **Hematology** will include but are not limited to the following: Basophils, Eosinophils, Hemoglobin, Lymphocytes, Monocytes, Neutrophils, Platelets, WBC, CRP and ESR.
- **Chemistry** will include but are not limited to the following: ALT, AST, Albumin, Alkaline Phosphatase, Bicarbonate (CO2), Calcium, Chloride, Creatinine, GGT, Glucose, Potassium, SGOT, SGPT, Sodium, Total Bilirubin, Total Protein, Urea Nitrogen.

Applicable laboratory results will be graded according to National Cancer Institute's Common Terminology Criteria for Adverse Events (NCI-CTCAE). The proportion of participants with post-baseline values by maximum toxicity grade for clinical laboratory tests will be summarized by study intervention group. Participants with toxicity grades  $\geq 2$  will be listed.

In addition, for selected laboratory parameters, LLN and ULN will also be used to identify abnormal laboratory test results, and the incidence and severity of abnormal laboratory parameters (hematology and chemistry) will be summarized by treatment group. Participants with maximum post-baseline elevated liver function tests through Week 20 relative to ULN will be summarized in categories as shown below will be provided.:

- $> 1$  to  $\leq 3$  x ULN
- $> 3$  to  $\leq 5$  x ULN
- $> 5$  to  $\leq 10$  x ULN
- $> 10$  to  $\leq 20$  x ULN

- $> 20 \times \text{ULN}$

In addition, Summary of potential Hy's Law case (ALT or AST  $\geq 3 \times \text{ULN}$  and total bilirubin  $\geq 2 \times \text{ULN}$  or INR  $> 1.5$ ) through Week 20 will also be provided.

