### **Screening Laboratory Test Parameters**

18. have screening laboratory test results within the following parameters. If one or more of the laboratory parameters is out of range, a single retest of laboratory values is permitted:
  - a. Hemoglobin  $\geq 10$  g/dL (SI:  $\geq 100$  g/L)
  - b. White blood cells  $\geq 3.5 \times 10^3/\mu\text{L}$  (SI:  $\geq 3.5$  GI/L)
  - c. Neutrophils  $\geq 1.5 \times 10^3/\mu\text{L}$  (SI:  $\geq 1.5$  GI/L)
  - d. Platelets  $\geq 100 \times 10^3/\mu\text{L}$  (SI:  $\geq 100$  GI/L)
  - e. Estimated glomerular filtration rate (eGFR)  $\geq 60$  mL/min/1.73 m^2

- f. Aspartate aminotransferase  $\leq 2 \times$  upper limit of normal (ULN)
- g. Alanine aminotransferase  $\leq 2 \times$  ULN
- h. Alkaline phosphatase  $\leq 2 \times$  ULN

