### **6.11. Appendix 10 Laboratory Toxicity Grading**

The grading scale use for lab assessments is based on ‘Common Terminology Criteria for Adverse Events (CTCAE) v5.0’.

If a laboratory value falls within the grading as specified below but also within the local laboratory normal limits, the value is considered to be normal and will be reset to grade 0.

Pre-baseline measurements will use the same grading ranges as applied to baseline measurements. In case a test has two sets of ranges – one for baseline normal and one for baseline abnormal, the one for baseline normal will be applied for all measurements taken pre-baseline and on baseline.

Text in gray italic in the table is present in the grading scale, but is not applied by Janssen when grading lab data.

| CTCAE Term                                      | Grade 1   | Grade 2  | Grade 3  | Grade 4  | Janssen implementation notes   |
|---|---|--|--|--|--|
| Blood and lymphatic system disorders     |   |  |  |  |  |
| Anemia  | Hemoglobin (Hgb)
<LLN - 10.0 g/dL;
<LLN - 6.2 mmol/L;
<LLN - 100 g/L             | Hemoglobin (Hgb)
<10.0 - 8.0 g/dL;
<6.2 - 4.9 mmol/L;
<100 - 80g/L                | Hemoglobin (Hgb) <8.0 g/dL;
<4.9 mmol/L;
<80 g/L;
transfusion indicated      | Life-threatening consequences;
urgent intervention indicated          | Clinical signs and symptoms are not taken into consideration for grading.  |
| Leukocytosis                                    | -   | -  | >100,000/mm  ;
>100 x 10  /L                                      | Clinical manifestations of leucostasis;
urgent intervention indicated | Clinical signs and symptoms are not taken into consideration for grading;
Added ranges in SI unit (x 10  /L)                  |
| Investigations                           |   |  |  |  |  |
| Activated partial thromboplastin time prolonged | >ULN - 1.5 x ULN  | >1.5 - 2.5 x ULN   | >2.5 x ULN;
bleeding   | -  | Clinical signs and symptoms are not taken into consideration for grading.  |

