| Alanine aminotransferase increased              | >ULN - 3.0 x ULN if baseline was normal;
1.5 - 3.0 x baseline if baseline was abnormal | >3.0 - 5.0 x ULN if baseline was normal;
>3.0 - 5.0 x baseline if baseline was abnormal | >5.0 - 20.0 x ULN if baseline was normal;
>5.0 - 20.0 x baseline if baseline was abnormal | >20.0 x ULN if baseline was normal;
>20.0 x baseline if baseline was abnormal | Ranges defined for “abnormal baseline” are applied only if baseline > ULN. If baseline < LLN, then ranges for “normal baseline” are applied. |
| Alkaline phosphatase increased                  | >ULN - 2.5 x ULN if baseline was normal;
2.0 - 2.5 x baseline if baseline was abnormal | >2.5 - 5.0 x ULN if baseline was normal;
>2.5 - 5.0 x baseline if baseline was abnormal | >5.0 - 20.0 x ULN if baseline was normal;
>5.0 - 20.0 x baseline if baseline was abnormal | >20.0 x ULN if baseline was normal;
>20.0 x baseline if baseline was abnormal | Ranges defined for “abnormal baseline” are applied only if baseline > ULN. If baseline < LLN, then ranges for “normal baseline” are applied. |
| Aspartate aminotransferase increased            | >ULN - 3.0 x ULN if baseline was normal;
1.5 - 3.0 x baseline if baseline was abnormal | >3.0 - 5.0 x ULN if baseline was normal;
>3.0 - 5.0 x baseline if baseline was abnormal | >5.0 - 20.0 x ULN if baseline was normal;
>5.0 - 20.0 x baseline if baseline was abnormal | >20.0 x ULN if baseline was normal;
>20.0 x baseline if baseline was abnormal | Ranges defined for “abnormal baseline” are applied only if baseline > ULN. If baseline < LLN, then ranges for “normal baseline” are applied. |
| Blood bilirubin increased                       | >ULN - 1.5 x ULN if baseline was normal;  | >1.5 - 3.0 x ULN if baseline was normal;   | >3.0 - 10.0 x ULN if baseline was normal;  | >10.0 x ULN if baseline was normal;  | Ranges defined for “abnormal baseline” are   |

| CTCAE Term                | Grade 1   | Grade 2  | Grade 3  | Grade 4  | Janssen implementation notes  |
|---------------------------|---|--|--|--|---|
|                           | > 1.0 - 1.5 x baseline if baseline was abnormal   | >1.5 - 3.0 x baseline if baseline was abnormal   | >3.0 - 10.0 x baseline if baseline was abnormal  | >10.0 x baseline if baseline was abnormal  | applied only if baseline > ULN. If baseline < LLN, then ranges for “normal baseline” are applied.   |

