| Hyperkalemia         | Potassium >ULN - 5.5 mmol/L  | Potassium >5.5 - 6.0 mmol/L;

intervention initiated  | Potassium >6.0 - 7.0 mmol/L;

hospitalization indicated   | Potassium >7.0 mmol/L;

life-threatening consequences   | Clinical signs and symptoms are not taken into consideration for grading. |
| Hypermagnesemia      | Magnesium >ULN - 3.0 mg/dL;
>ULN - 1.23 mmol/L  | -  | Magnesium >3.0 - 8.0 mg/dL;
>1.23 - 3.30 mmol/L   | Magnesium >8.0 mg/dL;
>3.30 mmol/L;

life-threatening consequences   | Clinical signs and symptoms are not taken into consideration for grading. |
| Hypernatremia        | Sodium >ULN - 150 mmol/L   | Sodium >150 - 155 mmol/L;

intervention initiated   | Sodium >155 - 160 mmol/L;

hospitalization indicated  | Sodium >160 mmol/L;

life-threatening consequences  | Clinical signs and symptoms are not taken into consideration for grading. |
| Hypertriglyceridemia | Triglycerides 150 mg/dL - 300 mg/dL;
1.71 mmol/L - 3.42 mmol/L  | Triglycerides >300 mg/dL - 500 mg/dL;
>3.42 mmol/L - 5.7 mmol/L   | Triglycerides >500 mg/dL - 1000 mg/dL;
>5.7 mmol/L - 11.4 mmol/L  | Triglycerides >1000 mg/dL;
>11.4 mmol/L;

life-threatening consequences  | Clinical signs and symptoms are not taken into consideration for grading. |
| Hypoalbuminemia      | Albumin <LLN - 3 g/dL;
<LLN - 30 g/L  | Albumin <3 - 2 g/dL;
<30 - 20 g/L   | Albumin <2 g/dL;
<20 g/L  | Life-threatening consequences;
urgent intervention indicated  | Clinical signs and symptoms are not taken into consideration for grading. |
| Hypocalcemia         | Corrected serum calcium of <LLN - 8.0 mg/dL;
<LLN - 2.0 mmol/L;

Ionized calcium <LLN - 1.0 mmol/L  | Corrected serum calcium of <8.0 - 7.0 mg/dL; <2.0 - 1.75 mmol/L;

Ionized calcium <1.0 - 0.9 mmol/L;                               | Corrected serum calcium of <7.0 - 6.0 mg/dL;
<1.75 - 1.5 mmol/L;

Ionized calcium <0.9 - 0.8 mmol/L;  | Corrected serum calcium of <6.0 mg/dL; <1.5 mmol/L;

Ionized calcium <0.8 mmol/L;  | Clinical signs and symptoms are not taken into consideration for grading. |

| CTCAE Term                         | Grade 1   | Grade 2  | Grade 3   | Grade 4   | Janssen implementation notes  |
|------------------------------------|---|--|---|---|---|

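### For laboratory tests graded on fixed ranges, the maximum-grade table and the Grade 2-or-higher listing cannot separate worsening from abnormality already present at baseline

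*SAP*

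**What the plan says.** SAP 5.6.3.1 plans these laboratory outputs:

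- A grade table: "The proportion of participants with post-baseline values by maximum toxicity grade for clinical laboratory tests will be summarized by study intervention group".
- A listing of individuals, "Participants with toxicity grades" of 2 or more.
- A summary of abnormal values against LLN and ULN for selected parameters.
- A liver table: "Participants with maximum post-baseline elevated liver function tests through Week 20 relative to ULN", in five bands starting at >1 to ≤3 x ULN.
- Continuous summaries: "Change from baseline through Week 20 will be summarized for chemistry, and hematology tests and displayed by intervention group".

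None of the categorical outputs is cross-classified by baseline or restricted to worsening.

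Grades follow "Common Terminology Criteria for Adverse Events (CTCAE) v5.0" as implemented in SAP Appendix 10. For ALT and AST, Grade 1 is "1.5 - 3.0 x baseline if baseline was abnormal"; ALP, GGT and bilirubin also have ranges relative to an abnormal baseline. Creatinine has a baseline term in Grades 2 and 3. Hemoglobin, neutrophils, platelets, WBC, lymphocytes, lipids and electrolytes have fixed ranges; for example, Grade 1 is "Triglycerides 150 mg/dL - 300 mg/dL". Where a test has two sets of ranges, Appendix 10 grades pre-baseline and baseline values on the normal-baseline set.

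Protocol 5.1, criterion 18, requires participants to "have screening laboratory test results within the following parameters". These are hemoglobin ≥10 g/dL, WBC ≥3.5, neutrophils ≥1.5 and platelets ≥100 (all x 10³/µL), eGFR ≥60, and ALT, AST and ALP ≤2 x ULN. The criterion has no limit for lymphocytes, lipids or electrolytes.

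**The concern.** A table of worst post-baseline grade is normally read as a description of what happened on treatment. If a participant's grade was the same before the first dose, that reading is wrong for that participant, and nothing planned in the SAP lets a reader see it. The change-from-baseline summaries and box plots are continuous and do not show how many participants moved up a grade.

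The SAP handles its other categorical safety data differently. Adverse events are restricted to treatment-emergent ones (5.6.2). Abnormal vital signs are labelled treatment-emergent, and the pulse and blood pressure criteria require a change from baseline as well as a threshold (5.6.3.2 and its Table 2). The C-SSRS has a baseline shift table (5.6.3.3).

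At stake is how readable the laboratory safety results are. Laboratory parameters and their change from baseline are an exploratory safety endpoint, and with arms of 30, 30 and 20 a few carried-over abnormalities can fill a row.

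**Working it through.** The plan gives no figure to reproduce here. The check applies the Appendix 10 rules to a participant whose post-baseline value equals the baseline value.

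**1. Unchanged values.** The documents give no LLNs, so those below are assumptions.

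| Test, same value before and after | Entry limit | Appendix 10 rule after baseline | Grade counted |
|---|---|---|---|
| Hemoglobin 10.5 g/dL (LLN 11.5 to 13.5) | ≥10 | Grade 1: below LLN to 10.0 | 1 |
| Neutrophils 1.6 (LLN 1.8 to 2.0) | ≥1.5 | Grade 1: below LLN to 1.5 | 1 |
| Platelets 110 (LLN 130 to 150) | ≥100 | Grade 1: below LLN to 75 | 1 |
| WBC 3.6 | ≥3.5 | Grade 1: below LLN to 3.0 | 1 if LLN is 4.0 to 4.5; 0 if LLN is 3.5 |
| Triglycerides >300 to 500 mg/dL | none | Grade 2: >300 to 500 | 2, and listed |
| ALT or AST 1.2 to 2.0 x ULN | ≤2 x ULN | Grade 1 needs 1.5 x baseline; ratio is 1.0 | 0 |
| ALP 1.2 to 2.0 x ULN | ≤2 x ULN | Grade 1 needs 2.0 x baseline; ratio is 1.0 | 0 |
| Bilirubin above ULN | none | Grade 1 needs >1.0 x baseline | 0 |

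The grade table therefore counts unchanged values for fixed-range tests but not for ALT, AST, ALP or bilirubin. GGT has the same Grade 1 rule as ALP.

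**2. Which rows are affected.** Grade 2 starts below 10.0 g/dL for hemoglobin, 1.5 for neutrophils, 75 for platelets and 3.0 for WBC. Each entry limit lies at or above that boundary, so eligible screening values are at most Grade 1. The Grade ≥2 rows and listing are exposed only for tests without an entry limit.

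**3. Liver table by multiples of ULN.** This table does not use the baseline-relative grades. An unchanged ALT of 1.8 x ULN falls in its >1 to ≤3 row. Entry stops at 2 x ULN for ALT, AST and ALP, so no unchanged eligible screening value on those tests reaches a higher row.

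**4. Size.** The documents give no baseline prevalence b, so b is assumed. The expected unchanged count is n x b. The SD of the chance difference in baseline prevalence between an active arm and placebo is √[b(1−b)(1/30 + 1/20)].

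| b | Active arm (30) | Placebo (20) | SD of chance difference |
|---|---|---|---|
| 5% | 1.5 | 1 | 6.3 points |
| 10% | 3 | 2 | 8.7 points |
| 20% | 6 | 4 | 11.5 points |

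**5. Dilution.** If every baseline abnormality persists and the true emergent rate is e, the table shows b + (1−b)e. Take e = 5% on placebo and 20% on active, purely for illustration; the true difference is 15 points.

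| b | Placebo | Active | Difference |
|---|---|---|---|
| 10% | 0.10 + 0.90 x 0.05 = 14.5% | 0.10 + 0.90 x 0.20 = 28.0% | 13.5 points |
| 20% | 0.20 + 0.80 x 0.05 = 24.0% | 0.20 + 0.80 x 0.20 = 36.0% | 12.0 points |
| 30% | 0.30 + 0.70 x 0.05 = 33.5% | 0.30 + 0.70 x 0.20 = 44.0% | 10.5 points |

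The difference shrinks by the factor 1−b. The ratio falls faster, from 4.0 to 1.9, 1.5 and 1.3, so ratios overstate the loss.

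**6. Whether one worsening rule fits every test.** An ALT of 1.8 x ULN at baseline is Grade 1 on the normal-baseline ranges. A rise to 5.2 x ULN is 5.2/1.8 = 2.9 x baseline, still Grade 1. A rule counting only grades above the baseline grade would call this no worsening, although it exceeds the 5 x ULN threshold in Protocol Appendix 6.

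**The case against.** The strongest reply is that Appendix 10 already deals with baseline where eligibility most openly admits abnormal values. ALT, AST and ALP are the tests admitted above ULN, and their post-baseline grades are relative to an abnormal baseline. This stands. A reader might infer that the grade table ignores baseline for every test; Appendix 10 shows that it does not for ALT, AST, ALP, GGT and bilirubin, and only partly for creatinine.

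Second, the hematology effect sits in the Grade 1 row, and a move from Grade 1 to Grade 2 still appears because the table is by grade. This also stands, but it does not help tests without an entry limit, where a Grade 2 entry may be new or may be unchanged.

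Third, the table is labelled post-baseline rather than treatment-emergent, safety has no formal comparison, and the randomized placebo arm shows the background rate. A reader might infer systematic bias between arms; randomization rules that out on average. With 30 against 20, however, the chance imbalance in step 4 is not small, and an unadjusted table carries much of it.

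Fourth, change from baseline is summarized, and clinically relevant laboratory changes are recorded as adverse events (Protocol 8.2.4). Both are useful, but neither gives the number whose grade worsened.

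Fifth, the liver table by ULN multiples is a sensible absolute-threshold complement to baseline-relative grades, in line with the protocol's liver criteria. That is a reason to keep it and show baseline alongside, not to remove it.

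**Conclusion.** The point holds for fixed-range tests. The grade table and the Grade ≥2 listing count abnormalities that were present before dosing and did not change, and no planned output separates these from worsening. The liver table by ULN multiples has the same feature, confined to its lowest row for unchanged ALT, AST and ALP values within the entry limit.

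The consequence is dilution and added noise in a descriptive display. No primary or secondary efficacy result is touched. The size depends on baseline prevalence and persistence, which the documents do not give; on the illustrative rates in step 5, a 15-point difference would show as 13.5 to 10.5 points. The hematology examples also rest on assumed LLNs, and the entry limits apply at screening, whereas baseline is the last value before the first dose. This is a low-cost improvement to the safety reporting rather than a defect that threatens the trial's conclusions.

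**What to change.** In SAP 5.6.3.1:

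1. Keep the maximum-grade table as planned.
2. For tests with fixed ranges in Appendix 10, add a shift table of baseline grade by worst post-baseline grade, and summarize by arm the participants whose grade worsened from baseline.
3. In the Grade ≥2 listing, show the baseline grade or a flag for abnormality at baseline. Remove no one from the listing.
4. Cross-tabulate the liver ULN categories by the baseline ULN category.
5. State that no rule based on exceeding the baseline grade applies to ALT, AST, ALP, GGT, bilirubin or creatinine. Baseline is graded on multiples of ULN and later values can be graded on multiples of baseline, so the two grades are not on one scale (step 6).

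Appendix 10 already says how baseline values are graded, so no new derivation rule is needed for the fixed-range tests. The cost is SAP wording and a few more standard tables, with no new data, visits or change to sample size.
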